14.1.18 Time to event variables

The protocol should state which of the following variables is used in that study.

14.1.19 Progression-free survival

Usually in all Oncology studies, patients are followed for tumor progression after discontinuation of study medication for reasons other than progression or death. If this is not used, e.g. in Phase I or II studies, this should be clearly stated in the protocol. Note that randomized trials (preferably blinded) are recommended where PFS is to be the primary endpoint.

Progression-free survival (PFS) is the time from date of randomization/start of treatment to the date of event defined as the first documented progression or death due to any cause. If a patient has not had an event, progression-free survival is censored at the date of last adequate tumor assessment.

14.1.20 Overall survival

All patients should be followed until death or until patient has had adequate follow-up time as specified in the protocol whichever comes first. The follow-up data should contain the date the patient was last seen alive / last known date patient alive, the date of death and the reason of death (“Study indication” or “Other”).

Overall survival (OS) is defined as the time from date of randomization/start of treatment to date of death due to any cause. If a patient is not known to have died, survival will be censored at the date of last known date patient alive.

14.1.21 Time to progression

Some studies might consider only death related to underlying cancer as an event which indicates progression. In this case the variable “Time to progression” might be used. TTP is defined as PFS except for death unrelated to underlying cancer.

Time to progression (TTP) is the time from date of randomization/start of treatment to the date of event defined as the first documented progression or death due to underlying cancer. If a patient has not had an event, time to progression is censored at the date of last adequate tumor assessment.

14.1.22 Time to treatment failure

This endpoint is often appropriate in studies of advanced disease where early discontinuation is typically related to intolerance of the study drug. In some protocols, time to treatment failure may be considered as a sensitivity analysis for time to progression. The list of discontinuation reasons to be considered or not as treatment failure may be adapted according to the specificities of the study or the disease.

Time to treatment failure (TTF) is the time from date of randomization/start of treatment to the earliest of date of progression, date of death due to any cause, or date of discontinuation due to reasons other than ‘Protocol violation’ or ‘Administrative problems’. The time to treatment failure for patients who did not experience treatment failure will be censored at last adequate tumor assessment.

14.1.23 Duration of response

The analysis of the following variables should be performed with much caution when restricted to responders since treatment bias could have been introduced. There have been reports where a treatment with a significantly higher response rate had a significantly shorter duration of response but where this probably primarily reflected selection bias which is explained as follows: It is postulated that there are two groups of patients: a good risk group and a poor risk group. Good risk patients tend to get into response readily (and relatively quickly) and tend to remain in response after they have a response. Poor risk patients tend to be difficult to achieve a response, may have a longer time to respond, and tend to relapse quickly when they do respond. Potent agents induce a response in both good risk and poor risk patients. Less potent agents induce a response mainly in good risk patients only. This is described in more detail by [Morgan \(1988\)](#)

It is recommended that an analysis of all patients (both responders and non-responders) be performed whether or not a “responders only” descriptive analysis is presented. An analysis of responders should only be performed to provide descriptive statistics and even then interpreted with caution by evaluating the results in the context of the observed response rates. If an inferential comparison between treatments is required this should only be performed on all patients (i.e. not restricting to “responders” only) using appropriate statistical methods such as the techniques described in [Ellis et al \(2008\)](#). It should also be stated in the protocol if duration of response is to be calculated in addition for unconfirmed response.

For summary statistics on “responders” only the following definitions are appropriate. (Specific definitions for an all-patient analysis of these endpoints are not appropriate since the status of patients throughout the study is usually taken into account in the analysis).

Duration of overall response (CR or PR): For patients with a CR or PR (which may have to be confirmed) the start date is the date of first documented response (CR or PR) and the end date and censoring is defined the same as that for time to progression.

The following two durations might be calculated in addition for a large Phase III study in which a reasonable number of responders is seen.

Duration of overall complete response (CR): For patients with a CR (which may have to be confirmed) the start date is the date of first documented CR and the end date and censoring is defined the same as that for time to progression.

Duration of stable disease (CR/PR/SD): For patients with a CR or PR (which may have to be confirmed) or SD the start and end date as well as censoring is defined the same as that for time to progression.

14.1.24 Time to response

Time to overall response (CR or PR) is the time between date of randomization/start of treatment until first documented response (CR or PR). The response may need to be confirmed depending on the type of study and its importance. Where the response needs to be confirmed then time to response is the time to the first CR or PR observed.

Although an analysis on the full population is preferred a descriptive analysis may be performed on the “responders” subset only, in which case the results should be interpreted with caution and in the context of the overall response rates, since the same kind of selection bias may be introduced as described for duration of response in [Section 14.1.23](#). It is recommended that an analysis of all patients (both responders and non-responders) be performed whether or not a “responders only” descriptive analysis is presented. Where an inferential statistical comparison is required, then all patients should definitely be included in the analysis to ensure the statistical test is valid. For analysis including all patients, patients who did not achieve a response (which may have to be a confirmed response) will be censored using one of the following options.

- at maximum follow-up (i.e. FPFV to LPLV used for the analysis) for patients who had a PFS event (i.e. progressed or died due to any cause). In this case the PFS event is the worst possible outcome as it means the patient cannot subsequently respond. Since the statistical analysis usually makes use of the ranking of times to response it is sufficient to assign the worst possible censoring time which could be observed in the study which is equal to the maximum follow-up time (i.e. time from FPFV to LPLV)
- at last adequate tumor assessment date otherwise. In this case patients have not yet progressed so they theoretically still have a chance of responding

Time to overall complete response (CR) is the time between dates of randomization/start of treatment until first documented CR. Similar analysis considerations including (if appropriate) censoring rules apply for this endpoint described for the time to overall response endpoint.

14.1.25 Definition of start and end dates for time to event variables

Assessment date

For each assessment (i.e. evaluation number), the **assessment date** is calculated as the latest of all measurement dates (e.g. X-ray, CT-scan) if the overall lesion response at that assessment is CR/PR/SD/UNK. Otherwise - if overall lesion response is progression - the assessment date is calculated as the earliest date of all measurement dates at that evaluation number.

Start dates

For all “time to event” variables, other than duration of response, the randomization/ date of treatment start will be used as the start date.

For the calculation of duration of response the following start date should be used:

- Date of first documented response is the assessment date of the first overall lesion response of CR (for duration of overall complete response) or CR / PR (for duration of overall response) respectively, when this status is later confirmed.

End dates

The end dates which are used to calculate ‘time to event’ variables are defined as follows:

- Date of death (during treatment as recorded on the treatment completion page or during follow-up as recorded on the study evaluation completion page or the survival follow-up page).
- Date of progression is the first assessment date at which the overall lesion response was recorded as progressive disease.
- Date of last adequate tumor assessment is the date the last tumor assessment with overall lesion response of CR, PR or SD which was made before an event or a censoring reason occurred. In this case the last tumor evaluation date at that assessment is used. If no post-baseline assessments are available (before an event or a censoring reason occurred) the date of randomization/start of treatment is used.
- Date of next scheduled assessment is the date of the last adequate tumor assessment plus the protocol specified time interval for assessments. This date may be used if back-dating is considered when the event occurred beyond the acceptable time window for the next tumor assessment as per protocol (see [Section 14.1.26](#)).

Example (if protocol defined schedule of assessments is 3 months): tumor assessments at baseline - 3 months - 6 months - missing - missing - PD. Date of next scheduled assessment would then correspond to 9 months.

- Date of discontinuation is the date of the end of treatment visit.
- Date of last contact is defined as the last date the patient was known to be alive. This corresponds to the latest date for either the visit date, lab sample date or tumor assessment date. If available, the last known date patient alive from the survival follow-up page is used. If no survival follow-up is available, the date of discontinuation is used as last contact date.

- Date of secondary anti-cancer therapy is defined as the start date of any additional (secondary) antineoplastic therapy or surgery.

14.1.26 Handling of patients with non-measurable disease only at baseline

It is possible that patients with only non-measurable disease present at baseline are entered into the study, either because of a protocol violation or by design (e.g. in Phase III studies with PFS as the primary endpoint). In such cases the handling of the response data requires special consideration with respect to inclusion in any analysis of endpoints based on the overall response evaluations.

It is recommended that any patients with only non-measurable disease at baseline should be included in the main (ITT) analysis of each of these endpoints.

Although the text of the definitions described in the previous sections primarily relates to patients with measurable disease at baseline, patients without measurable disease should also be incorporated in an appropriate manner. The overall response for patients with measurable disease is derived slightly differently according to Table 14-4.

Table 14-4 Overall lesion response at each assessment: patients with non-target disease only

Non-target lesions	New Lesions	Overall lesion response
CR	No	CR
Non-CR/Non-PD ¹	No	Non-CR/non-PD
UNK	No	UNK
PD	Yes or No	PD
Any	Yes	PD

¹ As defined in [Section 14.1.8](#).

In general, the **non-CR/non-PD response** for these patients is considered equivalent to an SD response in endpoint determination. In summary tables for best overall response patients with only non-measurable disease may be highlighted in an appropriate fashion e.g. in particular by displaying the specific numbers with the non-CR/non-PD category.

In considering how to incorporate data from these patients into the analysis the importance to each endpoint of being able to identify a PR and/or to determine the occurrence and timing of progression needs to be taken into account.

For ORR it is recommended that the main (ITT) analysis includes data from patients with only non-measurable disease at baseline, handling patients with a best response of CR as “responders” with respect to ORR and all other patients as “non-responders”.

For PFS, it is again recommended that the main ITT analyses on these endpoints include all patients with only non-measurable disease at baseline, with possible sensitivity analyses which exclude these particular patients. Endpoints such as PFS which are reliant on the determination and/or timing of progression can incorporate data from patients with only non-measurable disease.

14.1.27 Sensitivity analyses

This section outlines the possible event and censoring dates for progression, as well as addresses the issues of missing tumor assessments during the study. For instance, if one or more assessment visits are missed prior to the progression event, to what date should the progression event be assigned? And should progression event be ignored if it occurred after a long period of a patient being lost to follow-up? It is important that the protocol and RAP specify the primary analysis in detail with respect to the definition of event and censoring dates and also include a description of one or more sensitivity analyses to be performed.

Based on definitions outlined in [Section 14.1.25](#), and using the draft FDA guideline on endpoints (Clinical Trial Endpoints for the Approval of Cancer Drugs and Biologics, April 2005) as a reference, the following analyses can be considered:

Table 14-5 Options for event dates used in PFS, TTP, duration of response

Situation		Options for end-date (progression or censoring) ¹ (1) = default unless specified differently in the protocol or RAP	Outcome
A	No baseline assessment	(1) Date of randomization/start of treatment ³	Censored
B	Progression at or before next scheduled assessment	(1) Date of progression (2) Date of next scheduled assessment ²	Progressed Progressed
C1	Progression or death after exactly one missing assessment	(1) Date of progression (or death) (2) Date of next scheduled assessment ²	Progressed Progressed
C2	Progression or death after two or more missing assessments	(1) Date of last adequate assessment ² (2) Date of next scheduled assessment ² (3) Date of progression (or death)	Censored Progressed Progressed
D	No progression	(1) Date of last adequate assessment	Censored
E	Treatment discontinuation due to 'Disease progression' without documented progression, i.e. clinical progression based on investigator claim	(1) N/A (2) Date of discontinuation (visit date at which clinical progression was determined)	Ignored Progressed
F	New anticancer therapy given	(1) Date of last adequate assessment (2) Date of secondary anti-cancer therapy (3) Date of secondary anti-cancer therapy (4) N/A	Censored Censored Event Ignored
G	Deaths due to reason other than deterioration of 'Study indication'	(1) Date of last adequate assessment	Censored (only TTP and duration of response)

¹.=Definitions can be found in [Section 14.1.25](#)

².=After the last adequate tumor assessment. "Date of next scheduled assessment" is defined in Section 14.1.25.

³.=The rare exception to this is if the patient dies no later than the time of the second scheduled assessment as defined in the protocol in which case this is a PFS event at the date of death.

The primary analysis and the sensitivity analyses must be specified in the protocol. Clearly define if and why options (1) are not used for situations C, E and (if applicable) F.

Situations C (C1 and C2): Progression or death after one or more missing assessments: The primary analysis is usually using options (1) for situations C1 and C2, i.e.

- (C1) taking the actual progression or death date, in the case of only one missing assessment.
- (C2) censoring at the date of the last adequate assessment, in the case of two or more consecutive missing assessments.

In the case of two or missing assessments (situation C2), option (3) may be considered jointly with option (1) in situation C1 as sensitivity analysis. A variant of this sensitivity analysis consists of backdating the date of event to the next scheduled assessment as proposed with option (2) in situations C1 and C2.

Situation E: Treatment discontinuation due to ‘Disease progression’ without documented progression: By default, option (1) is used for situation E as patients without documented PD should be followed for progression after discontinuation of treatment. However, option (2) may be used as sensitivity analysis. If progression is claimed based on clinical deterioration instead of tumor assessment by e.g. CT-scan, option (2) may be used for indications with high early progression rate or difficulties to assess the tumor due to clinical deterioration.

Situation F: New cancer therapy given: the handling of this situation must be specified in detail in the protocol. However, option (1), i.e. censoring at last adequate assessment may be used as a default in this case.

Additional suggestions for sensitivity analyses

Other suggestions for additional sensitivity analyses may include analyses to check for potential bias in follow-up schedules for tumor assessments, e.g. by assigning the dates for censoring and events only at scheduled visit dates. The latter could be handled by replacing in [Table 14-5](#) the “Date of last adequate assessment” by the “Date of previous scheduled assessment (from baseline)”, with the following definition:

- **Date of previous scheduled assessment (from baseline)** is the date when a tumor assessment would have taken place, if the protocol assessment scheme was strictly followed from baseline, immediately before or on the date of the last adequate tumor assessment.

In addition, analyses could be repeated using the Investigators’ assessments of response rather than the calculated response. The need for these types of sensitivity analyses will depend on the individual requirements for the specific study and disease area and have to be specified in the protocol or RAP documentation.

14.1.28 Data handling and programming rules

The following section should be used as guidance for development of the protocol, data handling procedures or programming requirements (e.g. on incomplete dates).

14.1.29 Study/project specific decisions

For each study (or project) various issues need to be addressed and specified in the protocol or RAP documentation. Any deviations from protocol must be discussed and defined at the latest in the RAP documentation.

The proposed primary analysis and potential sensitivity analyses should be discussed and agreed with the health authorities and documented in the protocol (or at the latest in the RAP documentation before database lock).

14.1.30 End of treatment phase completion

Patients **may** voluntarily withdraw from the study treatment or may be taken off the study treatment at the discretion of the investigator at any time. For patients who are lost to follow-up, the investigator or designee should show "due diligence" by documenting in the source documents steps taken to contact the patient, e.g., dates of telephone calls, registered letters, etc.

The end of treatment visit and its associated assessments should occur within 7 days of the last study treatment.

Patients may discontinue study treatment for any of the following reasons:

- Adverse event(s)
- Lost to follow-up
- Physician decision
- Pregnancy
- Protocol deviation
- Technical problems
- Subject/guardian decision
- Death
- Progressive disease
- Study terminated by the sponsor
- Non-compliant with study treatment
- No longer requires treatment
- Treatment duration completed as per protocol (optional, to be used if only a fixed number of cycles is given)

14.1.31 End of post-treatment follow-up (study phase completion)

End of post-treatment follow-up visit will be completed after discontinuation of study treatment and post-treatment evaluations but prior to collecting survival follow-up.

Patients may provide study phase completion information for one of the following reasons:

- Adverse event
- Lost to follow-up
- Physician decision
- Pregnancy
- Protocol deviation
- Technical problems
- Subject/guardian decision

- Death
- New therapy for study indication
- Progressive disease
- Study terminated by the sponsor

14.1.32 Medical validation of programmed overall lesion response

As RECIST is very strict regarding measurement methods (i.e. any assessment with more or less sensitive method than the one used to assess the lesion at baseline is considered UNK) and not available evaluations (i.e. if any target or non-target lesion was not evaluated the whole overall lesion response is UNK unless remaining lesions qualified for PD), these UNK assessments may be re-evaluated by clinicians at Novartis or external experts. In addition, data review reports will be available to identify assessments for which the investigators' or central reader's opinion does not match the programmed calculated response based on RECIST criteria. This may be queried for clarification. However, the investigator or central reader's response assessment will never be overruled.

If Novartis elect to invalidate an overall lesion response as evaluated by the investigator or central reader upon internal or external review of the data, the calculated overall lesion response at that specific assessment is to be kept in a dataset. This must be clearly documented in the RAP documentation and agreed before database lock. This dataset should be created and stored as part of the 'raw' data.

Any discontinuation due to 'Disease progression' without documentation of progression by RECIST criteria should be carefully reviewed. Only patients with documented deterioration of symptoms indicative of progression of disease should have this reason for discontinuation of treatment or study evaluation.

14.1.33 Programming rules

The following should be used for programming of efficacy results:

14.1.34 Calculation of 'time to event' variables

Time to event = end date - start date + 1 (in days)

When no post-baseline tumor assessments are available, the date of randomization/start of treatment will be used as end date (duration = 1 day) when time is to be censored at last tumor assessment, i.e. time to event variables can never be negative.

14.1.35 Incomplete assessment dates

All investigation dates (e.g. X-ray, CT scan) must be completed with day, month and year.

If one or more investigation dates are incomplete but other investigation dates are available, this/these incomplete date(s) are not considered for calculation of the assessment date (and assessment date is calculated as outlined in [Section 14.1.25](#)). If all measurement dates have no day recorded, the 1st of the month is used.

If the month is not completed, for any of the investigations, the respective assessment will be considered to be at the date which is exactly between previous and following assessment. If a previous and following assessment is not available, this assessment will not be used for any calculation.

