7.2 Assessment types

7.2.1 Efficacy assessments

Tumor assessments are to be performed for screening purposes and are needed to determine the eligibility of the patient. Last available results of scans performed within 28 days prior to first dose of study drug will be used as baseline values. Negative scans at screening need not be repeated unless warranted by signs and symptoms suggesting disease progression. The assessment data will be collected until disease progression, unacceptable toxicity, death, protocol deviation or other reason that may leads to discontinuation or the end of study.

The following tumor assessments are to be performed and assessed prior to enrollment:

- Abdominal and pelvic triphasic CT or multiphase MRI;
- Chest X-ray (and/or chest CT if disease is present in chest).

To determine eligibility, measurable and non-measurable lesions must be assessed and target lesions identified prior to enrollment. For definition of measurable and target lesions please refer to RECIST 1.1 ([Appendix 1](#))

The same method of assessment and the same technique should be used to characterize each identified and reported lesion at baseline and after every 12 weeks while on-study. All radiology evaluations will be performed initially by the local radiologist.

Details of response assessment are provided in full protocol based on RECIST1.1, and are based exclusively on radiological findings obtained at tumor assessments.

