- d. A serum pregnancy test will be conducted locally at screening/baseline in all females of child-bearing potential, urine pregnancy test will be conducted at the end of treatment visit.
- e. Repeat scans (multiphase MRI or triphasic CT) at baseline and every 12 weeks thereafter. The same type of scan should be used at baseline and follow-up.
- f. Efficacy assessment will be collected until progression of disease (PD).
- g. If an investigator suspects a patient may be developing non-infectious pneumonitis, investigations such as pulmonary function tests, CT chest and referral to a pulmonologist should be considered.

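### A progression scan with no recorded month is discarded under protocol 14.1.35, so a documented PFS event can become a censoring

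*Protocol*

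**What the plan says.** Protocol 14.1.35 requires complete dates ("All investigation dates (e.g. X-ray, CT scan) must be completed with day, month and year") and then gives three rules for when they are not complete.

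- If some investigations at an assessment have full dates, "this/these incomplete date(s) are not considered for calculation of the assessment date".
- If no date at the assessment has a day, the first of the month is used.
- If the month is missing, "the respective assessment will be considered to be at the date which is exactly between previous and following assessment". Where that cannot be done, "If a previous and following assessment is not available, this assessment will not be used for any calculation".

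The rules stand under protocol 14.1.33, which opens with "The following should be used for programming of efficacy results".

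On how long scans go on, protocol 7.2.1 says "The assessment data will be collected until disease progression, unacceptable toxicity, death, protocol deviation or other reason" that may lead to discontinuation, or the end of the study. Footnote f of SAP Appendix 1, on scans in survival follow-up, says "Efficacy assessment will be collected until progression of disease (PD").

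SAP 5.5.2 bases PFS on the imaging date. It makes documented progression an event (Table 2 row 2), and also clinical progression without RECIST progression that ends treatment (row 3). It censors an event that falls more than 26 weeks after the last tumour assessment (row 7). The SAP imputes dates for diagnosis, medication, dosing, adverse event onset and death, but not for imaging.

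**The concern.** A midpoint needs an assessment on each side. The PD assessment is normally the last one collected, so it cannot get a midpoint and falls to the discard clause. The clause removes the whole assessment, not only its date. A patient with a documented progression then enters the PFS analysis as if it had not been seen.

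The loss is tied to the outcome. Dropping a PD assessment turns an event into an earlier censoring, or into a later death, and either change pushes the PFS curve up. PFS is a secondary endpoint, but it is one of the two efficacy results that the study was set up to give the regulator.

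**Working it through.** No figure in the plan depends on this rule: the sample size rests on feasibility and there is no target number of events. The check is therefore a reading of the rules followed by an illustration of size.

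**What happens to a PD assessment with no month on any investigation**

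1. Protocol 14.1.35: no following scan, so no midpoint, so the assessment is unused.
2. SAP Table 2 row 2 no longer has a documented progression to act on.
3. Row 3 makes it an event at treatment discontinuation only if an undated RECIST PD is taken to be clinical progression without RECIST progression, and only if it ended treatment. Scans continue into survival follow-up until PD, so a PD can be found after treatment stopped for another reason. Row 3 cannot cover that patient.
4. A later death is an event under row 6 only if row 7 does not censor it. The limit is 24 + 2 = 26 weeks from the last assessment. The last usable scan is about 12 weeks before the PD scan, so death must follow within about 26 − 12 = 14 weeks of the PD scan.
5. Otherwise the patient is censored at the previous scan.

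**Size**

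Inputs from the documents: about 60 patients; median PFS 11.04 months (the everolimus arm of the earlier phase III pNET trial cited in protocol 1.2.1.2); scans every 12 ± 1 weeks; the 26-week limit. Assumptions not in the documents: exponential PFS; 20% or 40% censored for other reasons; median survival after progression 24 months; 1% to 20% of last scans with no month; intermediate non-PD scans kept at their midpoint. Row 3 is not applied in the table. Kaplan-Meier results from 400,000 simulated patients, scaled to 60:

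| Other censoring | Last scans with no month | PDs lost per 60 | 12-month PFS, all dates known → rule applied | Points per lost PD |
|---|---|---|---|---|
| 20% | 1% | 0.47 | 0.492 → 0.495 | 0.3 / 0.47 = 0.6 |
| 20% | 2% | 0.93 | 0.493 → 0.498 | 0.5 / 0.93 = 0.5 |
| 20% | 5% | 2.32 | 0.493 → 0.506 | 1.3 / 2.32 = 0.6 |
| 20% | 10% | 4.66 | 0.491 → 0.518 | 2.7 / 4.66 = 0.6 |
| 20% | 20% | 9.38 | 0.491 → 0.548 | 5.7 / 9.38 = 0.6 |
| 40% | 5% | 1.67 | 0.481 → 0.493 | 1.2 / 1.67 = 0.7 |
| 40% | 10% | 3.38 | 0.481 → 0.506 | 2.5 / 3.38 = 0.7 |

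The base level is as expected. At 4.348 weeks per month, week 48 is 48 / 4.348 = 11.04 months and 12 months is 12 × 4.348 = 52.2 weeks. That lies between the week 48 and week 60 scans, so observed 12-month PFS should be close to 50%.

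The slope is plausible too. With no other censoring, one PD carries 1/60 = 1.7 points of the curve. About half of PDs fall before month 12, so the average gain is at most about 0.8 points, less the weight that Kaplan-Meier passes on to later events before month 12.

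The median is a poor gauge here. With 20% other censoring it stays at 11.2 months for 1% or 2% undated, then moves one scan step to 13.6 months at 5%, only because the plateau after week 48 lies just under 50%.

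**Row 3 applied to every lost PD** (discontinuation 0 to 2 weeks after the scan): at 5% undated, 12-month PFS goes 0.493 → 0.492 (20% other censoring) or 0.479 → 0.477 (40%). The upward bias is gone.

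**Last non-PD scans** are also dropped: 0.52 per 60 at 5% undated with 20% other censoring, against 2.32 PDs. Each such loss only moves a censoring date earlier.

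**The case against.** Much can be said for leaving this alone. Complete dates are mandatory, and protocol 9.4 has missing values queried with signed answers, so a scan with no month should be rare. Protocol 14.1.28 calls these rules guidance. Patients are treated until documented progression, so row 3 could restore most on-treatment events. PFS is descriptive in a single-arm safety study.

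The points on frequency and importance stand and keep this minor. The guidance point does not remove it: 14.1.33 directs the rules to be used, SAP section 7 records no departure from the protocol's methods, and the SAP sets its own rule for incomplete death dates (the 1st of the month, where protocol 14.1.36 uses the 15th) but none for scans. Row 3 stands only as a possible reading, since its wording describes patients without RECIST progression.

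A reader might infer more than the documents support:

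- That the rule removes only PD scans and keeps the rest. Collection also stops for toxicity and other reasons, so a last non-PD scan is dropped in the same way.
- That 14.1.35 contradicts itself, because its missing-month sentence speaks of any of the investigations. Read in order, the rule on complete dates takes every assessment with a usable date, and the missing-month rule covers what remains. The wording is loose, but there is a reading without conflict.
- That best response is distorted as well. SAP 5.5.3 uses the investigator's best response. Under protocol 14.1.17, a PD sets best response only within 12 weeks and without CR, PR or SD.
- That 14.1.35 contradicts Table 2 row 2. Row 2 dates a documented PD and 14.1.35 handles one that cannot be dated. The fault is a gap between them.

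**Conclusion.** The point holds in a narrow form, as a minor correction. A PD assessment with no month on any of its investigations is discarded by the only rule that covers it, and the SAP offers no replacement. Unless row 3 is read to include an undated RECIST PD, the event becomes a censoring at the previous scan, or a later death that row 7 may censor, and PFS is biased upward. A PD found after treatment stopped for another reason is exposed on any reading.

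The size is about 0.6 percentage points of 12-month PFS per lost PD with 20% other censoring (about 0.7 with 40%), and close to zero if row 3 rescues the event. This rests on an exponential median of 11.04 months and on assumed censoring and survival after progression. The missing-month rate is not given. At 1% of last scans, about half a PD per 60 patients would be lost and 12-month PFS would move by 0.3 points. Nothing in the documents supports the higher rates in the table, which show only the slope.

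**What to change.** Add to SAP 5.5.2, stated as overriding protocol 14.1.35:

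- (a) The missing-month rule applies only when no investigation at that assessment has a usable date.
- (b) An assessment rated PD is never discarded for an incomplete date. It remains a PFS event, dated at the visit date or scheduled date of that assessment, and bounded to fall after the previous assessment and no later than the next known date (end-of-treatment visit, new therapy or death).

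Part (b) is an exception to the SAP's use of imaging dates rather than visit dates and should be labelled as such. SAP section 7 should record the change.

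The cost is a sentence or two and a few lines of code. The downside is that such a patient's progression date is approximate. In the illustration, dating undated PDs at the scheduled visit left the median unchanged and 12-month PFS within 0.004 of its value with all dates known, at every missing rate tried.
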